# 16.12 End of Study (EOS)

The End of Study (EOS) visit must occur within 28 days of treatment discontinuation / completion (Week 103 Day 1) and prior to initiation of any new anti-cancer therapy/regimen. All patients discontinuing study treatment for any reason should undergo the following EOS procedures:

- 1. AE monitoring
- 2. Recording of concomitant medications
- 3. Vital signs and weight
- 4. Complete physical examination
- 5. ECOG performance status evaluation

- 6. Clinical laboratory values (hematology, coagulation, chemistry, urinalysis, *and both blood CEA/TA4 levels and thyroid function tests*)
- 7. Serum or urine pregnancy test for women of child-bearing potential
- 8. Research blood collection
- 9. Optional post-baseline tumor biopsy (only requested for patients with biopsy-accessible lesions and who discontinue from study prior to Week 10). Coagulation tests must be performed and evaluated within 24 hr prior to all biopsy procedures.
- 11. Radiographic evaluation of tumor burden and determination of response by RECIST v1.1 and iRECIST. See Appendices 5 and 6. Note: This is not required if confirmed PD is the reason for study discontinuation.

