#### 22.1.3 End of Treatment and Follow-Up Tumor Imaging

For participants who discontinue study treatment, tumor imaging should be performed at the time of treatment discontinuation (±4 week window). If previous imaging was obtained within 4 weeks prior to the date of discontinuation, then imaging at treatment discontinuation is not mandatory. For participants who discontinue study treatment due to documented disease progression, this is the final required tumor imaging if the investigator elects not to implement iRECIST.

For participants who discontinue study treatment without documented disease progression, every effort should be made to continue monitoring disease status by tumor imaging using the same imaging schedule used while on treatment (every 9 weeks) until the start of a new anticancer treatment, disease progression, pregnancy, death, withdrawal of consent, or the end of the study, whichever occurs first.

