#### 22.3 iRECIST Assessment of Disease

iRECIST is based on RECIST 1.1, but adapted to account for the unique tumor response seen with immunotherapeutic drugs. iRECIST will be used by the Investigator to assess tumor response and progression, and make treatment decisions. When clinically stable, participants should not be discontinued until progression is confirmed by the Investigator, working with local radiology, according to the rules outlined in Appendix 6. This allowance to continue treatment despite initial radiologic PD takes into account the observation that some participants can have a transient tumor flare in the first few months after the start of immunotherapy, and then experience subsequent disease response. This data will be captured in the clinical database.

Clinical stability is defined as the following:

- Absence of symptoms and signs indicating clinically significant progression of disease
- No decline in ECOG performance status
- No requirements for intensified management, including increased analgesia, radiation, or other palliative care

Any participant deemed **clinically unstable** should be discontinued from study treatment at site-assessed first radiologic evidence of PD, and is not required to have repeat tumor imaging for confirmation of PD by iRECIST.

If the Investigator decides to continue treatment, the participant may continue to receive study treatment and the tumor assessment should be repeated 4 to 8 weeks later to confirm PD by iRECIST, per Investigator assessment. Images should continue to be sent in to the central imaging vendor for potential retrospective BICR.

If repeat imaging does not confirm PD per iRECIST, as assessed by the Investigator, and the participant continues to be clinically stable, study treatment may continue and follow the regular imaging schedule. If PD is confirmed, participants will be discontinued from study treatment.

If a participant has confirmed radiographic progression (iCPD) as defined in Appendix 6, study treatment should be discontinued; however, if the participant is achieving a clinically meaningful benefit, an exception to continue study treatment may be considered following consultation with the Sponsor. In this case, if study treatment is continued, tumor imaging should continue to be performed following the intervals as outlined in the Schedule of Events (Appendix 1) and submitted to the central imaging vendor.

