A description of the adaptations and iRECIST process is provided in Appendix 6, with additional details in the iRECIST publication. A summary of imaging and treatment requirements after first radiologic evidence of progression is provided in Table 6 and illustrated as a flowchart in Figure 5.

Table 6. Imaging and Treatment after First Radiologic Evidence of Progressive Disease

[figure not shown]
	Clinically Stable		Clinically Unstable	
	Imaging	Treatment	Imaging	Treatment
First radiologic evidence of PD by RECIST 1.1 [For those studies in which PFS is the primary endpoint, add the following: that has been verified by BICR]	Repeat imaging at 4 to 8 weeks to confirm PD.	May continue study treatment at the Investigator's discretion while awaiting confirmatory tumor imaging by site by iRECIST.	Repeat imaging at 4 to 8 weeks to confirm PD per Investigator's discretion only.	Discontinue treatment
Repeat tumor imaging confirms PD (iCPD) by iRECIST per Investigator assessment	No additional imaging required.	Discontinue treatment (exception is possible upon consultation with Sponsor).	No additional imaging required.	Not applicable
Repeat tumor imaging shows iUPD by iRECIST per Investigator assessment	Repeat imaging at 4 to 8 weeks to confirm PD. May occur at next regularly scheduled imaging visit.	Continue study treatment at the Investigator's discretion.	Repeat imaging at 4 to 8 weeks to confirm PD per Investigator's discretion only.	Discontinue treatment
Repeat tumor imaging shows iSD, iPR, or iCR by iRECIST per Investigator assessment.	Continue regularly scheduled imaging assessments.	Continue study treatment at the Investigator's discretion.	Continue regularly scheduled imaging assessments.	May restart study treatment if condition has improved and/or clinically stable per Investigator's discretion.  Next tumor imaging should occur according to the regular imaging schedule.

Clinically Stable		Clinically Unstable	
Imaging	Treatment	Imaging	Treatment

BICR = Blinded Independent Central Review; iCPD = iRECIST confirmed progressive disease; iCR = iRECIST complete response; iRECIST = modified Response Evaluation Criteria in Solid Tumors 1.1 for immune-based therapeutics; iSD = iRECIST stable disease; iUPD = iRECIST unconfirmed progressive disease; PD = progressive disease; RECIST 1.1 = Response Evaluation Criteria in Solid Tumors 1.1.; VOP=verification of progression

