# GX-188E/Pembrolizumab [Protocol Number: GX-188E-005] Amended (V4.0)\_29Aug2022

[figure not shown]
17. Radiographic evaluations of tumor burden by RECIST v1.1 will be performed by a blinded independent central reviewer at Screening, approximately every 9 weeks during the treatment period, or more frequently as clinically indicated, and at End of Study if the reason for discontinuation is other than for confirmed radiologic disease progression. Scans obtained within 28 days prior to Week 1 Day 1 will be accepted for Screening and do not need to be repeated unless a clinically significant difference is suspected. Confirmatory scans are required approximately 4 weeks after any scan that indicates either an objective response, stable disease or disease progression,

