# **Evaluation of best overall response**

The best overall response is the best response recorded from the start of the study treatment until the end of treatment taking into account any requirement for confirmation. The patient's best overall response assignment will depend on the findings of both target and non-target disease, will also take into consideration the appearance of new lesions and will depend upon confirmatory scans. For this study, determinations of either CR, PR or PD require a confirmatory scan at least 4 weeks later. This is described further in Table B below.

Table B.Best Overall Response

Target Lesions	Non-Target Lesions	New Lesions	Overall Response	Best Response for this Category Also Requires
CR	CR	No	CR	≥4 weeks confirmation
CR	Non-CR/ Non-PD	No	PR	≥4 weeks confirmation
PR	Non-PD	No	PR	
SD	Non-PD	No	SD	documented at least once ≥4 weeks from baseline
PD	Any	Yes or No	PD	
Any	PD*	Yes or No	PD	no prior SD, PR or CR
Any	Any	Yes	PD	

\* In exceptional circumstances, unequivocal progression in non-target lesions may be accepted as disease progression

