#### 15. EFFICACY OUTCOMES

Tumor response to treatment will be evaluated using both RECIST v1.1 and iRECIST. For each patient with objectively measurable disease and who meet the criteria for inclusion in the Efficacy Evaluable population, response to therapy will be calculated. The analysis of ORR24, BORR and DCR per RECIST v1.1 will also be performed in safety population as sensitivity analysis.

RECIST 1.1 will be used by BICR as the primary measure for assessment of tumor response, date of disease progression, and as a basis for all protocol guidelines related to disease status (e.g., discontinuation of study treatment). All efficacy endpoints will be evaluated and categorized using RECIST 1.1. Confirmatory scans are required for all determinations of objective response [Partial response (PR) or Complete response (CR)], Stable disease (SD) and disease progression (PD). Confirmatory scans must be performed at least 4 weeks later.

Investigator assessment of tumor response based upon RECIST v1.1 will be analyzed in the same way as the corresponding BICR-assessed endpoints (except Kaplan-Meier curves which will only be presented for BICR assessment). Concordance between BICR and Investigator assessments will be summarized at a patient level for BOR.

iRECIST is based on RECIST 1.1, but adapted to account for the unique tumor response seen with immunotherapeutic drugs. iRECIST will be used by the investigator to assess tumor response and progression and make treatment decisions. When clinically stable, participants should not be discontinued until progression is confirmed by the Investigator, working with local radiology, according to the rules outlined in Appendix 6 of protocol. This allowance to continue treatment despite initial radiologic PD takes into account the observation that some participants can have a transient tumor flare in the first few months after the start of immunotherapy, and then experience subsequent disease response. This data will be captured in the clinical database.

Efficacy endpoints are as follows.

- Objective Response Rate within 24 weeks (ORR24)
- Best Overall Response Rate (BORR)
- Progression-Free Survival including 6-month PFS rate and median PFS time
- Overall Survival including 6-month OS rate and median OS time
- Disease Control Rate
- Duration of Response
- Time to Best Response

Document: \(\)\ieedc-vnac01\\Biosdata\\Genexine\\GX-188E\\GYA02599\\Biostatistics\\Documentation\\SAP\)

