Note: CR = complete response, PR = partial response, SD = stable disease, PD = progressive disease, and NE = not evaluable.

In the case of best response equal to SD, the minimum duration for SD should be met. In other words, there will be at least once overall response being SD or CR or PR after 28 days from the first dose of study medication. For example, if the first overall response is CR evaluated less than 28 days from the first dose, with subsequent overall response as PD, then the best overall response should be PD. If the first overall response is CR evaluated on or more than 28 days from the first dose, with subsequent overall response as PD, then the best overall response should be SD.

In the case of only one tumor assessment post dosing, if PD reported, the best overall response will be PD. Otherwise, if less than 28 days from the first dose, the best overall response should

 $Document: \underline{\label{locality} Nieedc-vnac01\\Biosdata\\Genexine\\GX-188E\\GYA02599\\Biostatistics\\Documentation\\SAParticles \\Documentation\\SAParticles \\Documentation\\SAParticles \\Documentation\\SAParticles \\Documentation\\SAParticles \\Documentation\\SAParticles \\Documentation\\SAParticles \\Documentation\\SAParticles \\SAParticles \\SAParti$ 

Author: [name] Version Number: 1.1

Version Date: 05Sep2022

Template No: CS\_TP\_BS016 Revision 6 Reference: CS\_WI\_BS005

Effective Date: 02Dec2019

<sup>a If a CR is truly met at first time point, then any disease seen at a subsequent time point, even disease meeting PR criteria relative to baseline, makes the disease PD at that point (since disease must have reappeared after CR). Best response would depend on whether minimum duration for SD was met. However, sometimes 'CR' may be claimed when subsequent scans suggest small lesions were likely still present and in fact the patient had PR, not CR at the first time point. Under these circumstances, the original CR should be changed to PR and the best response is PR.

Analysis Plan Page 30 of 48

be NE. If the only post dosing tumour assessment is 28 or more days from the first dose and overall response equal to CR or PR or SD, the best overall response will be SD, otherwise NE.

BICR-assessed ORR24 by RECIST v1.1 will be displayed for Part B and Part C.

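### The SAP contradicts itself on whether an unconfirmed RECIST 1.1 progression is a PFS or DOR event, and a repeat scan is not secured in clinically unstable patients

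*SAP*

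**What the plan says.** **Where confirmation of PD is required.** SAP section 15 states that all efficacy endpoints use RECIST 1.1. It then extends the repeat-scan rule beyond response to "Stable disease (SD) and disease progression (PD). Confirmatory scans must be performed at least 4 weeks later". The Statistical Methods note in the protocol synopsis has the same rule. Both Schedule of Events tables in Appendix 1 carry it as a footnote: "Confirmatory scans are required approximately 4 weeks after any scan that indicates either an objective response, stable disease or disease progression". The sponsor's note that opens Appendix 5 includes progression, and the best-overall-response text there says that "determinations of either CR, PR or PD require a confirmatory scan at least 4 weeks later".

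**Where the repeat scan is not secured.** Protocol 22.3, repeated in Appendix 6, says that a clinically unstable patient stops treatment at the first site-assessed PD and "is not required to have repeat tumor imaging for confirmation of PD by iRECIST". Table 6 gives, for the same patients, "Repeat imaging at 4 to 8 weeks to confirm PD per Investigator's discretion only". Protocol 22.1.3 says of the scan at discontinuation for progression that "this is the final required tumor imaging if the investigator elects not to implement iRECIST".

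**Where the SAP applies no confirmation to PD.** Table 2 in SAP 15.1 sets out confirmation for CR and PR only. The text after it says: "In the case of only one tumor assessment post dosing, if PD reported, the best overall response will be PD". In SAP 15.2, the DOR text refers simply to disease progression. PFS Table 3 counts documented progression as an event on its documented date. Neither mentions confirmation, and Table 3 has no row for an unconfirmed PD.

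**The concern.** PFS and DOR are among the endpoints listed in SAP section 15, so its confirmation sentence reaches them on its face. The rules that define those endpoints do not repeat it. Two programmers working from this SAP could treat the same unconfirmed PD differently: one as an event, the other as no event. Nor does the text settle whether a confirmed PD is dated at the first or the confirming scan. Appendix 5 backdates to the first scan only where the finding was initially equivocal.

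The patients affected are not a random subset. Those least likely to have a repeat scan are those who are clinically deteriorating at progression. Censoring them breaks the assumption behind the Kaplan-Meier estimates and moves median PFS, the 6-month PFS rate and DOR in the favourable direction. In a single-arm trial no control arm shares the bias, so it would go straight into any comparison with outside results.

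**Working it through.** The plan has no figure to reproduce here. The first step compares the rules; the second is an illustration.

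**Step 1. One patient under each rule.** Take a patient whose Week 10 scan was stable, who shows RECIST 1.1 PD at Week 19, is clinically unstable, stops treatment and has no further scan.

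| Rule applied | PFS status |
|---|---|
| SAP Table 3, with documented read as the first PD | Event at the Week 19 scan |
| SAP 15 confirmation rule | Progression not established: censored, or an event at death if death comes within the missed-assessment window and before new anti-cancer therapy |

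The missed-assessment window is 2 × 9 weeks = 126 days, as SAP 15.2 states.

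**Step 2. Size under the SAP 15 rule.** From the documents: scans every 9 weeks, so Days 64, 127, 190; a month of 30.4375 days (SAP section 9); the 126-day window. Assumptions not in the documents: exponential PFS with true median 3, 4 or 5 months; a share u of 20, 30 or 40% of PDs unconfirmed; post-progression median survival of 2 or 4 months in those patients; no new therapy.

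Six months is 6 × 30.4375 = 182.6 days, so only the scans at Days 64 and 127 count. With M the median in days, the chance of progression found at each scan is

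q1 = 1 − 0.5^(64/M), q2 = 1 − 0.5^(63/M).

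The 6-month PFS rate is (1 − q1)(1 − q2) if every PD counts. It is (1 − (1 − u)q1)(1 − (1 − u)q2) if unconfirmed PDs are censored at that scan and no deaths are counted.

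Example with median 3 months (M = 91.3) and u = 30%: q1 = 0.385 and q2 = 0.380.
- Every PD counts: 0.615 × 0.620 = 0.381.
- Unconfirmed PDs censored: (1 − 0.7 × 0.385)(1 − 0.7 × 0.380) = 0.731 × 0.734 = 0.536.

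6-month PFS with no deaths counted (upper bound):

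| True median | Every PD counts | 20% unconfirmed | 30% | 40% |
|---|---|---|---|---|
| 3 months | 38% | 48% | 54% | 59% |
| 4 months | 49% | 57% | 62% | 67% |
| 5 months | 56% | 64% | 68% | 72% |

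The rise is about 8 to 21 points.

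**Step 3. Counting deaths.** Under the same rule, a death within 126 days of the PD scan is a PFS event. With post-progression median survival of 2 months (60.9 days), 1 − 0.5^(126/60.9) = 76% of the unconfirmed patients die in the window. With 4 months (121.8 days) it is 51%. A large simulation that dates these events at death and censors the others at the PD scan gives:

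| True median | Every PD counts | 20% unconfirmed | 30% | 40% |
|---|---|---|---|---|
| 3 months | 38% | 42–44% | 44–47% | 45–50% |
| 4 months | 48% | 52–54% | 53–56% | 55–59% |
| 5 months | 56% | 59–61% | 60–63% | 62–65% |

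The rise is about 3 to 11 points. The bias shrinks but does not vanish: some patients outlive the window, and those who die are counted later than their PD scan.

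**The case against.** The strongest reply is that the operative rules already read correctly. Table 3 counts documented progression and has no censoring row for unconfirmed PD. DOR censoring is for patients continuing without progression or death. SAP 15.2 asks for confirmation of progression when it describes iRECIST, and Appendix 6 calls the first RECIST 1.1 PD unconfirmed only for iRECIST purposes. In Appendix 5, Table A assigns PD from a single time point, and the PD rows of Table B carry no 4-week entry. All of this stands, and it makes event at first PD the more natural reading. It does not remove the explicit sentence in SAP section 15, which covers every PD determination, and Table 3 does not define documented.

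A reader might infer something stronger: that unstable patients get no repeat scan and that their progressions can never become PFS or DOR events. The documents do not support this. The repeat scan is optional, and the Appendix 1 footnotes list one after any PD scan with no exception. Protocol 16.12 says of the End of Study scan, "This is not required if confirmed PD is the reason for study discontinuation", so it is still listed for a patient who stops at unconfirmed PD. That scan is not a dependable confirmation, because the visit falls within 28 days of discontinuation while confirmation needs at least 4 weeks from the PD scan. Protocol 22.1.3 also makes imaging at discontinuation non-mandatory if a scan was done in the previous 4 weeks. Even on the strict rule, a death inside the 126-day window and before new therapy is a PFS event.

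PFS and DOR are secondary and carry no hypothesis test. That limits the consequence but is no reason to leave the event undefined.

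**Conclusion.** The contradiction is real and is in the current text. The SAP states a confirmation rule for every RECIST 1.1 PD, its endpoint rules work without one, and the protocol does not secure the scan the rule would need in clinically unstable patients. It is therefore unsettled whether an unconfirmed PD is a PFS or DOR event and which scan dates it.

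Applying SAP section 15 as written would bias PFS and DOR upward. For 6-month PFS the illustration gives about 3 to 11 points with deaths counted, and about 8 to 21 points as an upper bound without them. Both ranges rest on assumed values for the unconfirmed share, the true median and survival after progression. If Table 3 is applied with documented meaning the first PD, there is no such bias. The point is one to settle before database lock. It is not evidence that the analysis will be biased, and it says nothing about the primary ORR24 analysis.

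**What to change.** For the PFS and DOR endpoints, remove PD from the RECIST 1.1 confirmation requirement in SAP section 15 and in the matching protocol text: the synopsis note, the two Appendix 1 footnotes, and the sponsor's note and best-overall-response paragraph in Appendix 5. State in SAP Table 3 and the DOR text that the event is the first RECIST 1.1 PD, confirmed or not, dated at that scan. Keep confirmation of progression for iRECIST (iCPD) only.

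Leave confirmation of SD out of this change: it bears on DCR and needs its own justification. The sponsor should also reconcile the imaging passages (Appendix 1 footnotes, 16.12, 22.1.3, 22.3 with Table 6, Appendix 6), which differ on whether a repeat scan is expected after PD.

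The cost is SAP and protocol wording, with no new data or patients. Reported PFS and DOR may look slightly less favourable than under the confirmation rule.

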#### **15.1.** PRIMARY EFFICACY ENDPOINTS

The primary efficacy variable is BICR-assessed ORR24 by RECIST 1.1 in Part B and C.

Best overall response within 24 weeks (BOR24) is the best objective response achieved within the first 24 weeks of treatment prior to study discontinuation. All available response designations will contribute to the BOR24 determination. If a patient's BOR24 could not be confirmed, that patient will not be included in the primary efficacy population for ORR24. Additional patients will be enrolled to meet the study hypothesis. Any CR or PR must be confirmed by a sequential assessment that is at least 4 weeks apart. The confirmation rule is defined in Table 2 (please refer to RECIST 1.1 [1]). The confirmed response will be determined before analysis. The number and percentage of patients in each category of best overall response CR, PR, SD, PD or Not Evaluable (NE) will be provided.

ORR24 is the proportion of efficacy evaluable patients who achieve an objective response (PR or CR) within 24 weeks prior to study discontinuation. The number and percentage of patients who achieve best overall response of PR or CR will be summarized.

If the first responses can be confirmed by the second response within 24 weeks of treatment. they will be included as responses for ORR24. Also, If the first response within 24 weeks is confirmed by the second response after 24 weeks of treatment, the first response should be included as response for ORR24.

Table 2. Best overall response when confirmation of CR and PR is required per RECIST 1.1 Guideline

Overall response  First time point	Overall response Subsequent time point	Best overall response
CR	CR	CR
CR	PR	PR, or SD provided at least 28 days' duration, otherwise PD a
CR	SD	SD provided at least 28 days' duration, otherwise PD

Document: \(\)\ieedc-vnac01\\Biosdata\\Genexine\\GX-188E\\GYA02599\\Biostatistics\\Documentation\\SAP\)

Author: [name] Version Number: 1.1

Version Date: 05Sep2022

Template No: CS TP BS016 Revision 6 Reference: CS WI BS005

Analysis Plan Page 29 of 48

CR	PD	SD provided at least 28 days' duration, otherwise PD
CR	NE	SD provided at least 28 days' duration, otherwise NE
PR	CR	PR
PR	PR	PR
PR	SD	SD
PR	PD	SD provided at least 28 days' duration, Otherwise PD
PR	NE	SD provided at least 28 days' duration, Otherwise NE
NE	NE	NE

Note: CR = complete response, PR = partial response, SD = stable disease, PD = progressive disease, and NE = not evaluable.

In the case of best response equal to SD, the minimum duration for SD should be met. In other words, there will be at least once overall response being SD or CR or PR after 28 days from the first dose of study medication. For example, if the first overall response is CR evaluated less than 28 days from the first dose, with subsequent overall response as PD, then the best overall response should be PD. If the first overall response is CR evaluated on or more than 28 days from the first dose, with subsequent overall response as PD, then the best overall response should be SD.

In the case of only one tumor assessment post dosing, if PD reported, the best overall response will be PD. Otherwise, if less than 28 days from the first dose, the best overall response should

 $Document: \underline{\label{locality} Nieedc-vnac01\\Biosdata\\Genexine\\GX-188E\\GYA02599\\Biostatistics\\Documentation\\SAParticles \\Documentation\\SAParticles \\Documentation\\SAParticles \\Documentation\\SAParticles \\Documentation\\SAParticles \\Documentation\\SAParticles \\Documentation\\SAParticles \\Documentation\\SAParticles \\SAParticles \\SAParti$ 

Author: [name] Version Number: 1.1

Version Date: 05Sep2022

Template No: CS\_TP\_BS016 Revision 6 Reference: CS\_WI\_BS005

Effective Date: 02Dec2019

<sup>a If a CR is truly met at first time point, then any disease seen at a subsequent time point, even disease meeting PR criteria relative to baseline, makes the disease PD at that point (since disease must have reappeared after CR). Best response would depend on whether minimum duration for SD was met. However, sometimes 'CR' may be claimed when subsequent scans suggest small lesions were likely still present and in fact the patient had PR, not CR at the first time point. Under these circumstances, the original CR should be changed to PR and the best response is PR.

Analysis Plan Page 30 of 48

be NE. If the only post dosing tumour assessment is 28 or more days from the first dose and overall response equal to CR or PR or SD, the best overall response will be SD, otherwise NE.

BICR-assessed ORR24 by RECIST v1.1 will be displayed for Part B and Part C.

In Part C, BICR-assessed ORR24 by RECIST v1.1 will be calculated for patients overall. 95% confidence interval for ORR24 will be estimated using exact Clopper-Pearson method. In Part C, it will be analyzed using two-sided exact binomial test for a null hypothesis for ORR24 of P0 = 12.2% with a significance level of 0.05.

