#### 15.2 Prohibited Concomitant Medications

Medications or vaccinations specifically prohibited in the exclusion criteria are not allowed during the ongoing trial. If there is a clinical indication for any medication or vaccination specifically prohibited during the trial, discontinuation from study intervention or vaccination may be required. The investigator is to discuss prohibited medication/vaccination with the Sponsor's Clinical Director. The final decision on any supportive therapy or vaccination rests with the investigator and/or the participant's primary physician. However, the decision to continue the participant on study treatment requires the mutual agreement of the investigator, the Sponsor and the participant.

Listed below are specific restrictions for concomitant therapy or vaccination during the course of the study: (Note: There are no prohibited therapies during the post-treatment long-term follow-up period).

- Anti-cancer systemic chemotherapy or biological therapy other than those specified in the protocol (GX-188E, pembrolizumab)
- Immunotherapy not specified in this protocol
- Chemotherapy not specified in this protocol
- Investigational agents other than Use of investigational therapeutic agents than those specified in the protocol (i.e., investigational regimen; GX-188E, pembrolizumab).
- Radiation therapy
  - Note: Radiation therapy to a symptomatic solitary lesion, to the brain, or for palliative purposes may be allowed after consultation with Sponsor Medical Monitor.
- Live or live attenuated vaccines within 30 days prior to the first dose of trial treatment and while participating in the trial.

Note: Administration of killed vaccines are allowed.

Note: Any licensed COVID-19 vaccine (including for Emergency use) in a particular country is allowed in the study as long as they are mRNA vaccines, adenoviral vaccines, or inactivated vaccines. These vaccines will be treated just as any other concomitant therapy. Investigational vaccines (i.e., those not licensed or approved for Emergency Use) are not allowed.

• Systemic glucocorticoids for any purpose other than to modulate symptoms from an event of clinical interest of suspected immunologic etiology. The use of physiologic doses of corticosteroids may be approved after consultation with the Sponsor Medical Monitor. *Topical and inhaled steroids are permitted*.

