#### 19.0 Discontinuation/Withdrawal criteria

# 19.1 **Discontinuation of Study Treatment**

Discontinuation of study treatment does not represent withdrawal from the study.

A participant must be discontinued from study treatment but continue to be monitored in the study for any of the following reasons:

- Recurrent Grade 2 pneumonitis
- Discontinuation of treatment may be considered for participants who have attained a confirmed complete response (CR) and have been treated for at least 8 pembrolizumab cycles (at least 24 weeks), including 2 doses of pembrolizumab beyond the date when the initial CR was declared.
- Completion of 35 treatments (approximately 2 years) with pembrolizumab. Note: The number of treatments is calculated starting with the first dose of pembrolizumab.

The reasons a patient may discontinue or be withdrawn from the study include, but are not limited to, adverse events, disease progression, patient request, Investigator decision, protocol violation, patient noncompliance, and study termination by the Sponsor.

When a patient discontinues or is withdrawn, the Investigator will notify the Sponsor (or designee) and should perform the procedures indicated in the EOS column in the Schedule of Events (Appendix 1) within 28 days after discontinuation of study drug and prior to initiation of any therapy.

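### The BOR24 rule behind the primary endpoint has no cut-off at RECIST 1.1 progression, so a partial response that follows progression can be counted in ORR24

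*SAP*

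**What the plan says.** **Which assessments count.** SAP 15.1 defines BOR24 as the best objective response "within the first 24 weeks of treatment prior to study discontinuation" and adds that "All available response designations will contribute to the BOR24 determination". A first response inside 24 weeks may be confirmed by a scan after 24 weeks.

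**Where the window ends.** Protocol 19.1 states that "Discontinuation of study treatment does not represent withdrawal from the study", so the study-discontinuation limit does not coincide with stopping treatment or with progression. Protocol Appendix 5 defines best overall response as "the best response recorded from the start of the study treatment until the end of treatment". Neither text names progression as the end.

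**What happens after first PD.** Under Protocol 22.3, if the investigator continues treatment, "the participant may continue to receive study treatment and the tumor assessment should be repeated 4 to 8 weeks later". The images still go to the central vendor. The reason given is flare: "This allowance to continue treatment despite initial radiologic PD takes into account the observation that some participants can have a transient tumor flare".

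**How sequences are scored.** SAP Table 2 starts its rows with CR, PR or NE. The notes below it cover PD after an initial CR and PD as the only post-dose assessment. They do not cover PD followed by response.

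**The concern.** RECIST 1.1 and iRECIST differ mainly in how they treat shrinkage after a first progression, and the primary endpoint is meant to be the RECIST 1.1 one. If the instruction to use all designations is programmed as written, a patient with PD at Week 10 and a confirmed PR afterwards can enter the numerator of ORR24. The same patient could have a PFS event at Week 10 and be a RECIST 1.1 responder at Week 19.

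The omission affects response only: the SAP has rules for subsequent therapy in PFS and DOR, but no stopping rule of any kind for BOR24. The gap can only add responders. It bears on a success rule that compares ORR24 with a fixed 12.2%, and one patient can decide the result.

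**Working it through.** **1. Can the sequence fall inside the window?** The first scan is about 9 weeks after treatment starts (the Week 10 visit). A repeat scan 4 to 8 weeks later falls at Weeks 14 to 18, and the next scheduled scan is at Week 19. Both are before Week 24, and confirmation may come later still. So PD at Week 10, then PR by Week 19, then a confirming scan fits ORR24.

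**2. Which progressions can be followed by a RECIST 1.1 PR?** In Appendix 5, Table A, any new lesion at a time point makes that time point PD. A flare with persisting new lesions therefore cannot become PR. What remains is target-lesion PD, non-target PD, or new lesions that later resolve. A target-lesion case must move from at least 20% above the smallest sum to at least 30% below baseline by Week 24. That is a narrow group.

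**3. The plan's own figure.** Inputs from Protocol 24.3: null rate 12.2%, alternative 37%, two-sided 0.05, power 97%, dropout 25%, N=60. Success requires the lower two-sided 95% Clopper-Pearson bound to exceed 12.2%.
- Evaluable n: 60 × 0.75 = 45.
- Lower bound for x of n: the 2.5% quantile of Beta(x, n − x + 1). For 10/45 it is 11.2% (fails); for 11/45 it is 12.9% (passes). The threshold is 11.
- Power: P(X ≥ 11 | n=45, 0.37) = 0.974. The plan's 97% and N=60 reproduce.

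Protocol 24.8 and SAP 4.3 describe the final analysis on 60 efficacy-evaluable patients, and Protocol 10.5 gives 45 to 60, so I also use n=60. There 13/60 has a lower bound of 12.1% (fails) and 14/60 has 13.4% (passes). The threshold is 14.

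**4. Illustration: a fixed number of added responders (assumption).** Suppose k patients who would otherwise be non-responders are counted because of a post-PD PR. With threshold r, the chance of success under a true 12.2% becomes P(X ≥ r − k).

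| k | n=45, r=11 | n=60, r=14 |
|---|---|---|
| 0 | 1.7% | 1.2% |
| 1 | 4.2% | 2.7% |
| 2 | 9.1% | 5.7% |

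**5. Illustration: a shift in the rate (assumption).** Suppose post-PD responses raise the null rate by a few percentage points.

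| Shift | n=45 | n=60 |
|---|---|---|
| 0 | 1.7% | 1.2% |
| 1 point | 2.9% | 2.2% |
| 2 points | 4.7% | 3.9% |
| 3 points | 7.0% | 6.3% |

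The nominal upper-tail level is 2.5%. Planned N, alpha and power do not change if a cut-off is added; only the classification of patients does.

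**The case against.** **A reader might infer that the plan scores PD, PR, PR as a RECIST 1.1 response. The documents do not go that far.** Table 2 is silent on PD-first sequences. Appendix 5, Table B attaches to a best response of PD the condition that no SD, PR or CR came before it. Read literally, a patient whose first assessment is PD has best response PD. Appendix 6 lists response after RECIST 1.1 PD among the features of iRECIST and wants the two best responses recorded separately. Post-PD images go to the vendor only for possible retrospective central reading. All this stands, and it shows what was probably intended. But no text applies it to BOR24, and the one general instruction in SAP 15.1 points the other way.

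**PD confirmation.** SAP 15 and Protocol Appendix 5 require a confirming scan for PD. On that reading a PD followed by PR was never a confirmed PD, and counting the PR would be correct. SAP 15.1, however, accepts a single unconfirmed PD as best response when it is the only assessment. The objection exposes a second ambiguity, which any new wording must settle.

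**New therapy.** A reader might also infer that responses to later treatment leak into ORR24. This is mostly closed. Other anticancer therapy is prohibited on treatment (Protocol 15.2), the End of Study visit precedes new therapy (16.12), and scheduled imaging ends when it starts (22.1.2, 22.1.3). What remains is stray scans and one permitted exception: "Radiation therapy to a symptomatic solitary lesion, to the brain, or for palliative purposes may be allowed after consultation with Sponsor Medical Monitor". The SAP has no rule for response scans after such radiation.

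**Conclusion.** The point holds as a gap in the primary-endpoint definition. Followed literally, SAP 15.1 can put a post-PD response into the RECIST 1.1 endpoint, while Appendix 6 places it under iRECIST.

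The size is unknown. Few patients can be affected, and the documents give no rate of post-PD response. The step from 1.7% to 4.2% (n=45) or from 1.2% to 2.7% (n=60) assumes exactly one added responder in a trial with a true rate of 12.2%. A reader might take these figures as the trial's actual type I error; they are not. How far the comparison with 12.2% is distorted also depends on how the benchmark study scored responses after progression, which the documents do not say. What needs no assumption about frequency is that one patient separates failure at 10/45 from success at 11/45, and that the gap works only toward success.

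**What to change.** In SAP 15.1, replace the sentence on available designations with:

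> BOR24 and BOR by RECIST 1.1 use BICR assessments up to and including the first RECIST 1.1 PD, dated at the first scan showing PD whether or not later confirmed, and before any subsequent anticancer therapy. Later responses count only in iRECIST endpoints.

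Add a PD-first row to Table 2 with best response PD. Reconcile the new wording with the PD-confirmation statement in SAP 15, so that one definition of PD governs BOR24. The new-therapy clause is only a safeguard for stray scans; the SAP should also say whether permitted palliative radiation falls under it.

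The cost is SAP wording and programming. ORR24 may come out slightly lower. Sample size, alpha and planned power stay as they are.
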